9.5 Statistical Methods

9.5.1 Statistical Methods for Immunogenicity Analyses

This section describes the statistical methods that address the primary and secondary immunogenicity objectives.

Immunogenicity analyses will be conducted for each serotype separately.

Primary Endpoints/Hypotheses (H1 and H2)

The first primary objective (to compare the serotype-specific OPA GMTs at 30 days postvaccination with V116 versus PPSV23) will be assessed via the 2 hypotheses.

For the 12 common serotypes, the primary noninferiority hypothesis (H1) regarding OPA GMT levels between recipients of V116 and PPSV23 is:

H0: $\text{GMT1}/\text{GMT2} \leq 0.50$ versus

H1: $\text{GMT1}/\text{GMT2} > 0.50$

where GMT1 is the serotype-specific OPA GMT for the V116 group and GMT2 is the serotype-specific OPA GMT for the PPSV23 group. A ratio of 0.50 corresponds to an OPA GMT that is 2.0-fold lower in the V116 group compared with the PPSV23 group. Rejecting the null hypothesis (H0) at the 1-sided $\alpha=0.025$ level corresponds to the lower bound of the 2-sided 95% CI on the GMT ratio (V116/PPSV23) being >0.50 and would lead to the conclusion that the OPA response to V116 for the common serotype is noninferior to that of PPSV23.

For the 9 serotypes that are unique to V116, the primary superiority hypothesis (H2) regarding OPA GMT levels between recipients of V116 and PPSV23 is:

H0: $\text{GMT1}/\text{GMT2} \leq 2.0$ versus

H1: $\text{GMT1}/\text{GMT2} > 2.0$

where GMT1 is the serotype-specific OPA GMT for the V116 group, and GMT2 is the serotype-specific OPA GMT for the PPSV23 group. A ratio of 2.0 corresponds to an OPA GMT that is 2.0-fold higher in the V116 group compared with the PPSV23 group. Rejecting the null hypothesis (H0) at the 1-sided $\alpha=0.025$ level corresponds to the lower bound of the 2-sided 95% CI on the GMT ratio (V116/PPSV23) being >2.0 and would lead to the conclusion that the OPA response to V116 for the unique serotype is superior to that of PPSV23.

To address the first primary immunogenicity objective, the serotype-specific OPA GMTs at 30 days postvaccination will be compared between vaccination groups. The GMT ratio estimation, 95% CI, and the hypothesis test (ie, 1-sided p-value) will be calculated using a cLDA method proposed by Liang and Zeger [Liang, K-Y and Zeger, S. L. 2000] using data from both vaccination groups. In this model, the response vector consists of the log-transformed antibody titers at baseline and 30 days postvaccination. This model allows the inclusion of participants who are missing either the baseline or postbaseline measurements, thereby increasing efficiency.

Secondary Endpoints

A similar statistical model as used for the first primary objective will be used to address the secondary objective that compares the serotype-specific IgG GMCs at 30 days postvaccination with V116 compared with PPSV23.

Descriptive statistics with point estimates and within-group 95% CIs will be provided for all other immunogenicity endpoints. For the continuous endpoints, the point estimates will be calculated by exponentiating the estimates of the mean of the natural log values and the within-group CIs will be derived by exponentiating the bounds of the CIs of the mean of the natural log values based on the t-distribution. For the dichotomous endpoints, the within-group CIs will be calculated based on the exact method proposed by Clopper and Pearson [Clopper, C. J. and Pearson, E. S. 1934].

Reverse Cumulative Distribution Curves for both OPA titers and IgG concentrations at 30 days postvaccination will be graphically displayed by serotype.

A detailed analysis strategy for immunogenicity endpoints is listed in [Table 4](#).

Table 4 Analysis Strategy for Immunogenicity Variables

Endpoint/Variable (Description, Time Point)	Primary vs Supportive Approach ^a	Statistical Method	Analysis Population	Missing Data Approach
Primary Endpoints				
OPA GMTs at 30 days postvaccination for the 12 common serotypes in V116 and PPSV23	P	cLDA (estimate, 95% CI, p-values)	PP	Model-based
	S		FAS	
OPA GMTs at 30 days postvaccination for the 9 unique serotypes in V116	P	cLDA (estimate, 95% CI, p-values)	PP	Model-based
	S		FAS	
Secondary Endpoints				
IgG GMCs at 30 days post vaccination for the 1) 12 common serotypes between V116 and PPSV23 2) 9 unique serotypes in V116	P	cLDA (estimate, 95% CI)	PP	Model-based
GMFRs and proportions of participants with a ≥4-fold rise from baseline to 30 days postvaccination for 1) serotype-specific OPA responses and 2) serotype-specific IgG responses within each vaccination group	P	Descriptive Statistics (estimate, 95% CI)	PP	Missing data will not be imputed
CI=confidence interval; cLDA=constrained longitudinal data analysis; FAS=full analysis set; GMC=geometric mean concentration; GMFR=geometric mean fold rise; GMT=geometric mean titer; IgG=immunoglobulin G; OPA=opsonophagocytic activity; PP=per-protocol. ^a P=Primary approach; S=Supportive approach.				

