4 STUDY DESIGN

4.1 Overall Design

This is a Phase 3, randomized, double-blind, active comparator-controlled clinical study to evaluate the safety, tolerability, and immunogenicity of V116 in children and adolescents aged ≥ 2 to < 18 years who have completed a primary pneumococcal vaccination regimen and who are at increased risk of pneumococcal disease (ie, chronic heart disease, chronic lung disease, diabetes mellitus, chronic liver disease, or chronic kidney disease).

Approximately 820 participants will be randomized in a 3:2 ratio to receive a single dose of either V116 or PPSV23 on Day 1. Randomization will be stratified by the number of increased-risk conditions for pneumococcal disease (1 increased-risk condition, or ≥ 2 increased-risk conditions) and by prior pneumococcal vaccination and age:

- Prior PCV7 alone
- Prior PCV7 and one prior PPSV23 dose
- Prior PCV10 alone and ≥ 2 to < 6 years old
- Prior PCV10 alone and ≥ 6 to < 18 years old
- Prior PCV10 and one prior PPSV23 dose
- Prior PCV13 alone and ≥ 2 to < 6 years old
- Prior PCV13 alone and ≥ 6 to < 18 years old
- Prior PCV13 and one prior PPSV23 dose

Note: Participants who previously received a combination of PCV7, PCV10, and/or PCV13 or any doses of PCV15 or PCV20 will be excluded from this study.

Participants are to have ≥ 1 increased-risk condition listed in Inclusion Criteria #1 (Section 5.1). It is expected that ≥ 25 participants per risk condition will be enrolled. In participants with ≥ 2 increased-risk conditions, each condition will count towards the total per condition.

Participants risk condition(s) must be considered stable for ≥ 3 months with no anticipated major change in treatment expected for the duration of the study and with ≤ 1 hospitalization directly related to the risk condition within 3 months before study vaccination.

An eVRC will be used by the participant/participant's legally authorized representative to record solicited injection-site AEs, solicited systemic AEs, and daily body temperatures from Day 1 through Day 5 after vaccination. Unsolicited AEs will also be recorded from Day 1 through Day 30 after vaccination. The participant/participant's legally authorized representative will be provided an electronic device or have their own electronic device configured, if compatible, to complete the eVRC.

Blood samples for immunogenicity assays will be drawn on Day 1 (Visit 1) and Day 30 (Visit 3).

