4.2 Scientific Rationale for Study Design

This study will evaluate the safety, tolerability, and immunogenicity of V116 in children and adolescents ≥ 2 to < 18 years of age who have completed a primary pneumococcal vaccination regimen and who are at increased risk for pneumococcal disease.

Children and adolescents with one or more stable chronic medical conditions, including chronic heart disease, chronic lung disease, diabetes mellitus, chronic liver disease, and chronic kidney disease will be included in this study. The population of children and adolescents with these chronic medical conditions are at increased risk for IPD and were selected for inclusion based on their overall prevalence in the pediatric population (Section 2.1).

The randomization ratio of 3:2 was chosen to increase the number of participants exposed to V116 to expand the V116 safety and immunogenicity data in a population at increased risk for pneumococcal disease.

Participants will be stratified by prior PCV regimen received in infancy and prior PPSV23 vaccination, as prior pneumococcal vaccination may impact immune responses to V116 and PPSV23 for the shared serotypes. Participants will also be stratified by the number of risk conditions (1 increased-risk condition only or ≥ 2 increased-risk conditions) as it is expected that the number of participants enrolled with 1 or more conditions will vary and to ensure balance between the intervention groups. Participants will also be stratified by age (≥ 2 to < 6 and ≥ 6 to < 18 years of age) for those who received PCV10 and PCV13 alone to ensure balance between the intervention groups.

Individuals with severe heart, liver, lung, or kidney disease, and those with uncontrolled diabetes will be excluded from this study to allow them to prioritize their medical care over participation in this study and to avoid associating the effects of medical treatment with the safety and immunogenicity of the vaccine.

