6.3.2 Stratification

Intervention randomization will be stratified according to the following factors:

- Prior pneumococcal vaccination and age:
 - Prior PCV7 alone
 - Prior PCV7 and one prior PPSV23 dose
 - Prior PCV10 alone and ≥ 2 to < 6 years old
 - Prior PCV10 alone and ≥ 6 to < 18 years old
 - Prior PCV10 and one prior PPSV23 dose
 - Prior PCV13 alone and ≥ 2 to < 6 years old
 - Prior PCV13 alone and ≥ 6 to < 18 years old
 - Prior PCV13 and one prior PPSV23 dose
- Number of increased-risk conditions for pneumococcal disease (including chronic heart disease or chronic lung disease or diabetes mellitus or chronic liver disease, and/or chronic kidney disease):
 - 1 increased-risk condition
 - ≥ 2 increased-risk conditions*

*Note: The participant must meet the inclusion/exclusion criteria for each of the increased-risk conditions in order to be included in this stratum.

It is expected that ≥ 25 participants per risk condition listed in Inclusion Criteria #1 (Section 5.1) will be enrolled. In participants with ≥ 2 increased-risk conditions, each condition will count towards the 25 total per condition.

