9 KEY STATISTICAL CONSIDERATIONS

This section outlines the statistical analysis strategy and procedures for the study; further details will be provided in the SAP. If, after the study has begun, but prior to any unblinding/final database lock, changes are made to primary and/or key secondary hypotheses, or the statistical methods related to those hypotheses, then the protocol will be amended (consistent with ICH Guideline E9). Changes to exploratory or other nonconfirmatory analyses made after the protocol has been finalized, but prior to any unblinding/final database lock, will be documented in the SAP and referenced in the CSR for the study. Post hoc exploratory analyses will be clearly identified in the CSR.

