9.8 Sample Size and Power Calculations

9.8.1 Sample Size and Power for Immunogenicity Analyses

The study will randomize approximately 820 participants, allocated in a 3:2 ratio to receive either V116 or PPSV23 (492 participants in the V116 group and 328 participants in the PPSV23 group).

Primary Immunogenicity Endpoints/Hypotheses (H1 and H2)

For the primary hypotheses, this study has >90% power to declare noninferiority of V116 to PPSV23 for the 12 common serotypes (H1) and superiority of V116 to PPSV23 for the 9 unique serotypes (H2) at an overall 1-sided 2.5% alpha-level.

The sample size and power calculations are based on the following assumptions:

- For the 12 common serotypes, the underlying serotype-specific OPA GMT ratios (V116/PPSV23) and the standard deviation of natural log-transformed OPA results are assumed to be the same as that observed in the V116-004 Phase 3 study. The OPA GMT ratios range from 0.84 to 1.74. The standard deviations range from 0.93 to 1.43 for V116 and range from 0.96 to 1.43 for PPSV23.
- For the 9 unique serotypes, the underlying serotype-specific OPA GMT ratios (V116/PPSV23) and the standard deviation of natural log-transformed OPA results are assumed to be the same as that observed in the V116-004 Phase 3 study. The OPA GMT

ratios range from 2.90 to 23.72. The standard deviations range from 1.03 to 1.52 for V116 and range from 1.05 to 2.54 for PPSV23.

- 90% evaluability (443 participants in the V116 group and 295 participants in the PPSV23 group).

Based on the assumptions above, the power for the primary hypotheses is calculated using a simulation-based approach. This approach uses the cLDA model for comparing OPA GMTs between the 2 vaccination groups. The power is estimated as the number of successful iterations out of the total iterations in the simulation. The success within each iteration is defined as meeting both primary hypotheses for each serotype (ie, noninferiority for the 12 common serotypes [H1] and superiority for the 9 unique serotypes [H2]).

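### The primary cLDA and its power simulation are described without the randomisation strata; leaving them out would cost precision, by an amount the documents do not let one determine

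*Combined protocol and SAP*

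**What the plan says.** **Design.** Section 6.3.2 states: "Intervention randomization will be stratified according to the following factors". It then lists eight levels combining prior pneumococcal vaccination with age, and two levels for the number of risk conditions. Section 4.1 gives the same scheme. Section 4.2 offers a prognostic reason for the vaccination factor: "prior pneumococcal vaccination may impact immune responses to V116 and PPSV23 for the shared serotypes". For age the reason is different: participants are stratified "for those who received PCV10 and PCV13 alone to ensure balance between the intervention groups". For the number of conditions the reasons are expected variation in enrolment and balance. Neither of these two factors is said to predict response.

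**Analysis.** Section 9.5.1 specifies a cLDA fitted to both groups: "In this model, the response vector consists of the log-transformed antibody titers at baseline and 30 days postvaccination". Table 4 lists the method simply as cLDA, and the IgG comparison is to use a similar model. No stratification factor is named in Section 9.

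**Power.** In Section 9.8.1: "This approach uses the cLDA model for comparing OPA GMTs between the 2 vaccination groups". The listed inputs are GMT ratios, SDs and 90% evaluability. Success requires every serotype to pass: "The success within each iteration is defined as meeting both primary hypotheses for each serotype".

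**Deferral.** Section 9 introduces itself as an outline and says "further details will be provided in the SAP". The supplied text has no separate SAP section giving model terms.

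**The concern.** When a trial stratifies its randomisation, the usual analysis conditions on the same factors. If it does not, variance between strata stays in the model's error term. Baseline titer is already in the response vector and will absorb part of any prior-vaccination effect, so what matters is how far strata predict Day-30 titer beyond baseline.

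Two consequences need to be kept apart:

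- **Efficiency.** Without the strata the confidence interval is wider than it need be, however the allocation turned out.
- **Calibration.** If allocation is also balanced within strata, the estimate varies less than the unadjusted model believes. The model SE is then too large and the 1-sided test runs below 0.025. Without such balance the unadjusted SE is valid but inefficient.

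At stake is the width of 21 reported intervals, and a small amount of power in a trial where all 21 tests must succeed.

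**Working it through.** **1. The plan's own figures.** 820 × 3/5 = 492 and 820 × 2/5 = 328; at 90% evaluability these become 443 and 295, as stated. The joint power of >90% can be neither reproduced nor refuted: Section 9.8.1 gives only ranges of ratios and SDs, without serotype pairing or baseline correlation.

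**2. H1 worst stated case.** Ratio 0.84, SD 1.43 in both arms, no credit for baseline:

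- ln(0.84/0.5) = 0.519
- SE = 1.43 × √(1/443 + 1/295) = 0.1075
- power = Φ(0.519/0.1075 − 1.96) = 99.8%

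**3. Assumed inputs.** R² is the share of Day-30 log-titer variance explained by strata, and r is the within-stratum baseline/Day-30 correlation. The documents give neither. I use R² = 0, 5, 10, 20% and r = 0.4, with the same covariance and the same stratum effects in both arms. With complete data the cLDA then behaves like an ANCOVA on baseline.

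**4. Interval width, unadjusted relative to adjusted.**

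- Strata act equally at both time points: the total slope on baseline is b = R² + r(1 − R²), and w = √[(1 − b²) / ((1 − R²)(1 − r²))].
- Strata act at Day 30 only: w = √[(1 − r²(1 − R²)) / ((1 − R²)(1 − r²))].

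**5. True 1-sided error of the unadjusted test when strata are balanced.** This is 1 − Φ(1.96k), where k is model SE divided by true SE.

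- Both time points: k = √[(1 − b²) / ((1 − R²)(1 + b² − 2br))]. This is slightly smaller than w, because the unadjusted slope b differs from the within-stratum slope r.
- Day 30 only: k = w.

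Example, R² = 20%, both time points: b = 0.20 + 0.4 × 0.80 = 0.52; w = √(0.7296/0.672) = 1.042; k = √(0.7296/0.6835) = 1.033; error = 1 − Φ(2.025) = 2.14%.

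| R² | Both: CI wider by | Both: true error | Day 30 only: CI wider by | Day 30 only: true error |
|---|---|---|---|---|
| 0 | 0 | 2.50% | 0 | 2.50% |
| 5% | 1.1% | 2.39% | 3.1% | 2.17% |
| 10% | 2.1% | 2.29% | 6.4% | 1.85% |
| 20% | 4.2% | 2.14% | 13.9% | 1.28% |

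At R² = 20% with r from 0.2 to 0.6, the widths are 2.5 to 6.5% (both) and 12.3 to 17.9% (Day 30 only). Day 30 only is a larger scenario, not a bound: equal and opposite stratum effects at the two times (R² = 20%, r = 0.4) give w = √[(1 − 0.12²)/0.672] = 1.21.

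**6. Role of balance.** A simulation with 738 participants, 16 cells of assumed size and r = 0.5 set strata to explain 10, 20 and 30% of the variance left after baseline. With 3:2 blocks within cells and no stratum terms, model SE over empirical SE was 1.07, 1.09 and 1.20. Without blocks it was 0.995 to 1.00: the unadjusted SE was correct for its own estimator, but up to about 18% larger than the adjusted SE.

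**7. Power.** Because all 21 tests must pass, joint power >90% means each single test exceeds 90%. Take an unadjusted test whose actual power is 90% under balanced strata. In units of the adjusted SE its effect is 1.96w + 1.2816w/k, and adjusted power is Φ(1.96w + 1.2816w/k − 1.96). At r = 0.4 with strata acting at both times, this gives 90.4, 90.8 and 91.5% for R² = 5, 10 and 20%. That is a gain of 0.4 to 1.5 points from the lowest possible start.

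**8. Cost if strata predict nothing.** The additive terms number (8 − 1) + (2 − 1) = 8 per time point. With unblocked allocation, chance imbalance inflates the SE by roughly √(1 + 8/738) = 1.005, about 0.5%. With blocked strata a simulation gave about 0.09%.

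**The case against.** The strongest objection is that the quoted sentence defines the outcomes, not the model. It lists no explanatory terms at all, not even vaccination group or time, so the absence of strata says little, and the SAP may already contain them. That stands: what the text establishes is a gap in specification, and every consequence above is conditional on the strata being left out. It does not dispose of the point. Section 9 requires a protocol amendment if the methods for the primary hypotheses change after the study begins, so the terms of the primary model are worth fixing in the protocol text. As written, two analysts could fit different models and both comply.

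Three stronger readings are tempting, and the documents do not support them.

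- **The test necessarily runs below 0.025.** Section 4.2 intends balance, but no section states blocks, and without balance within strata the unadjusted SE is valid.
- **The >90% power is in doubt.** The stated reason to expect prognostic strata concerns the shared serotypes, where the worst stated case already has 99.8% power. For the unique serotypes the lowest ratio, 2.90, gives 90.2% with SD 1.52 in both arms and 61.7% with 1.52 and 2.54, before any credit for baseline. The plan does not pair ratios with SDs, and nothing says strata predict those responses.
- **All the strata are prognostic.** Section 4.2 says so, and only as a possibility, for prior vaccination alone.

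The objection that R² could be zero also stands. In that case nothing is lost by omitting the strata, and almost nothing by including them.

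**Conclusion.** The point holds as an improvement in precision and prespecification, not as a threat to validity. If the cLDA is fitted without the stratification factors, the estimated GMT ratio is unbiased and Type I error is at or below its nominal level, but the interval is wider than necessary. The size is unknown. Under the assumptions above (r = 0.4, R² of 5 to 20%, common covariance and stratum effects across arms) the excess width is 1.1 to 4.2% if strata act equally at both times and 3.1 to 13.9% if they act at Day 30 only. The true error rates of 2.39 to 2.14% and 2.17 to 1.28% additionally require balance within strata. For the shared serotypes the benefit is narrower reported intervals rather than power. For the unique serotypes a power gain arises only if strata predict those responses, which no section states. The change is still worth making, because the possible gain exceeds the cost and all 21 tests must succeed.

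**What to change.** - In Section 9.5.1, Table 4 and the SAP, list the cLDA terms and include both stratification factors as randomised, entered additively and each by time point, in the OPA and IgG models.
- Add a simple rule, applied blind to vaccination group, for combining levels only if some prove too small. No stratum counts are given, so a detailed pooling scheme is not needed now.
- In Section 9.8.1, state whether the power simulation uses this same model or leaves the strata out.

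The cost is a few sentences and about eight extra parameters per time point, with an SE increase under 0.6% if strata predict nothing. No new data are needed: Section 6.3.1 randomises centrally through the IRT, so the strata should be on record for every randomised participant.

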9.5.2 Statistical Methods for Safety Analyses

Safety and tolerability will be assessed by clinical review of all relevant parameters, including AEs and postvaccination temperature measurements.

9.5.2.1 Overall Safety Assessment

The overall safety evaluation will include a summary by vaccination group (V116 group and PPSV23 group) of the number and percentage of participants with any AEs, any unsolicited AEs, any vaccine-related AEs, any SAEs, any vaccine-related SAEs, and any AEs resulting in death after vaccination. Point estimates and 95% CIs for the between-group differences (V116 compared with PPSV23) in the percentages of participants with the event will be provided for these events.

The number and percentage of participants with specific AEs will also be provided. Point estimates and 95% CIs for the differences between vaccination groups in the percentages of participants with specific AEs will be provided for solicited AEs and AEs that occur in $\geq 2\%$ of participants in the V116 group or PPSV23 group.

The number and percentage of participants with maximum temperature measurements meeting the Brighton Collaboration cut points [Marcy, S. M., et al 2004] will be provided along with point estimates and 95% CIs of between-group differences.

CIs for between-group differences will be provided using the M&N method [Miettinen, O. and Nurminen, M. 1985]. Rainfall plots with point estimates and 95% CIs will be displayed for AEs that occur in $\geq 5\%$ of participants in the V116 group or PPSV23 group.

A detailed analysis strategy for safety endpoints is listed in [Table 5](#).

Table 5 Analysis Strategy for Safety Parameters

Analysis Part	Safety Endpoint	Descriptive Statistics	Between-group 95% CI	Graphical Display
Overall Safety Assessment	Solicited injection-site AE (Day 1 through Day 5 postvaccination) ^a	X	X	
	Solicited systemic AE (Day 1 through Day 5 postvaccination) ^a	X	X	
	Any AE ^b	X	X	
	Any unsolicited AE ^b	X	X	
	Any vaccine-related AE ^b	X	X	
	Any SAE ^b	X	X	
	Any vaccine-related SAE ^b	X	X	
	Death ^b	X	X	
	Specific AEs by SOC and PT ^c	X	X	X
Maximum temperatures (Day 1 through Day 5 postvaccination) ^d	X	X		

AE=adverse event; CI=confidence interval; PT=preferred term; SAE=serious adverse event; SOC=system organ class.

^a Solicited injection-site AEs include redness (erythema), swelling (swelling), and pain and tenderness (pain); solicited systemic AEs include muscle aches all over body (myalgia), headache (headache), tiredness (fatigue), hives or welts (urticaria), irritability (irritability), joint pain (arthralgia), drowsiness (somnolence), feeling sick (malaise), fever (pyrexia). Note: Daily temperatures will be solicited Day 1 through Day 5 postvaccination. Elevated temperatures of $\geq 100.4^{\circ}\text{F}$ ($\geq 38.0^{\circ}\text{C}$) will be categorized as solicited events of pyrexia.

^b These endpoints are broad AE categories. For example, descriptive statistics for the safety endpoint of “Any AE” will provide the number and percentage of participants with at least 1 AE.

^c Descriptive statistics, 95% Between-group CI, and Graphical Display will be provided for specific AEs with an incidence $>0\%$, $\geq 2\%$, and $\geq 5\%$ of participants, respectively, in each vaccination group.

^d Maximum temperature measurements are categorized by Brighton Collaboration cut points.

